8.3.15 Androgen receptor (AR) quantification

The method for quantifying androgen receptor (AR) density from harvested prostate tissue is similar to that described in Section 8.3.3, and will rely on immunohistochemical staining for the AR protein. This endpoint will be expressed as the mean staining percentage in tumor tissue.

8.3.16 Pathological complete responses (pCR)

This will be defined as the absence of tumor identification by the study pathologist on standard histological analysis of the resected prostate specimens. The endpoint will be expressed as the proportion of men achieving a pCR.

8.3.17 PSA response rates

This will be defined as the proportion of patients who achieve an undetectable PSA (<0.1 ng/mL) by 3 months after prostatectomy. The endpoint will be expressed as the proportion of men achieving a PSA response.

8.3.18 Time to PSA recurrence

This will be defined as the interval from the time of prostatectomy to the time when the serum PSA is ≥ 0.2 ng/mL. PSA will be measured approximately 1 month after prostatectomy, and every 3 (±1) months during the first post-operative year and every 6 (±2) months during the second and third post-operative years. For subjects who have not yet demonstrated PSA relapse at the time of censoring, patients will be censored at the date of

the last assessment that shows a lack of PSA recurrence. This outcome will be expressed as a median and will be determined using the Kaplan-Meier method.

8.3.19 In expansion cohort (Amendment 1): assessment of Gleason grade change (prostatectomy Gleason sum vs. core biopsy Gleason sum) post neoadjuvant Enoblituzumab treatment

This will be defined by comparing highest Gleason grade from pre-treatment biopsy versus highest Gleason grade from post-treatment prostatectomy. This endpoint will be expressed as the proportion of men achieving a Gleason score change.

8.3.20 Global expression profiling of pre and post treatment tumor tissue using single cell RNA sequencing, the immune NanoString immunopanel and/or microarrays

Expression profiling will be conducted as per established protocols for single cell RNA seq, Nanostring, and microarray

8.3.21 IHC analyses of CD137, CD16 and/or CD107A across potential immune infiltrate following Enoblituzumab

CD137, CD107A, and CD16 expression in prostate tumor specimens will be assessed by IHC in the prostatectomy surgical specimens (post-treatment). This endpoint will be expressed as the mean staining percentage of each of these in in tumor tissue.

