Target population	 Inclusion criteria Histologically confirmed prostate adenocarcinoma Clinical stage T1c-T3b, N0, M0 Gleason sum 7-10 At least 2 positive cores Prior decision to undergo radical prostatectomy Adult male ≥18 years of age ECOG performance status 0-1, or Karnofsky score ≥ 70% Adequate kidney, liver, and bone marrow function Willingness to sign informed consent and adhere to study requirements Exclusion criteria: Presence of known lymph node involvement or distant metastases Prior radiation, hormones, biologics, or chemotherapy for prostate cancer Prior use of experimental agents for prostate cancer Prior use of experimental agents for prostate cancer History of autoimmune disease requiring systemic immunosuppression History of other malignancy within 3 years Uncontrolled major infectious, cardiovascular, pulmonary, hematologic, or psychiatric illnesses that would make the patient a poor study candidate

IRB#: IRB0010377

Johns Hopkins University

Start date/Initial patients are expected to be entered in November 2016. With an estimatedDurationenrollment rate of 3 patients per month, accrual is expected to last 5-6 months.

The trial was originally designed to evaluate safety and PD endpoint with 16 patients. Based on promising PSA response data prior to prostatectomy, following Enoblituzumab therapy alone, the study will enroll an additional 16 patients for a total size of 32 – amendment 1. All patients will be enrolled utilizing identical inclusion, exclusion, and treatment conditions as the first 16 patients. Expanding the trial to enroll a total of 32 patients will provide statistical power to estimate the clinical benefit of Enoblituzumab in terms of undetectable PSA level (<0.1 ng/mL) 12 months following radical prostatectomy.

Sample size 16 evaluable patients (*i.e.* those that undergo prostatectomy)

16 additional patients in the expansion Amendment 1 will be enrolled for a total sample size of 32 patients.

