	•Global expression profiling of pre and post treatment tumor tissue				
	using single cell RNA sequencing, the immune NanoString immunopanel				
	and/or Affy microarrays				
Table 1 Study Calendar	Footnote C: These labs should be collected prior to treatment.				
8.2.2 In expansion cohort	•All subjects receiving at least one dose of the study drug will be				
(amendment 1)	assessed for PSA ₀ Response Rate (Undetectable PSA level <0.1 ng/mL)				
	at 12 months following radical prostatectomy				
8.3.4 PD-L1 expression	PD-L1 expression in prostate tumor specimens will be assessed by IHC				
	be expressed as the mean staining percentage of PD-L1 in tumor tissue.				
8.3.7					
	•				
	as the mean staining percentage in tumor tissue.				
8.3.19	In expansion cohort (Amendment 1): assessment of Gleason grade				
	change (prostatectomy Gleason sum vs. core biopsy Gleason sum) post				
	neoadjuvant Enoblituzumab treatment				
8.3.7	 in the primary core specimens (pre-treatment) and in the prostatectomy surgical specimens (post-treatment). This endpoint will be expressed as the mean staining percentage of PD-L1 in tumor tissue. Mean NK cell density in tumor tissue from harvested prostate glands of patients. The method for quantifying NK cell density from harvested prostate tissue is as described in Section 8.3.3. This endpoint will be expressed as the mean staining percentage in tumor tissue. In expansion cohort (Amendment 1): assessment of Gleason grade change (prostatectomy Gleason sum vs. core biopsy Gleason sum) post 				

	This will be defined by comparing highest Gleason grade from pre- treatment biopsy versus highest Gleason grade from post-treatment prostatectomy. This endpoint will be expressed as the proportion of men achieving a Gleason score change.			
8.3.20	Global expression profiling of pre and post treatment tumor tissue using single cell RNA sequencing, the immune NanoString immunopanel and/or microarrays Expression profiling will be conducted as per established protocols for single cell RNA seq, Nanostring, and microarray			
8.3.21	IHC analyses of CD137, CD16 and/or CD107A across potential immune infiltrate following Enoblituzumab CD137, CD107A, and CD16 expression in prostate tumor specimens will be assessed by IHC in the prostatectomy surgical specimens (post- treatment). This endpoint will be expressed as the mean staining percentage of each of these in in tumor tissue.			

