1.2 Secondary Objectives

- To quantify markers of apoptosis (TUNEL staining, caspase 3 staining, FcGamma staining) in prostate tumor specimens of treated patients.
- To quantify markers of cell proliferation (Ki-67) in prostate tumor specimens of treated patients.
- To quantify the extent of CD8⁺ T cell infiltration into the prostate from harvested prostate glands of treated patients.
- To quantify the extent of PD-L1+ cell density in the prostate from harvested prostate glands of treated patients.
- To quantify the extent of CD4+ T cell and T_{reg} infiltration into the prostate in prostate specimens of treated patients.
- To quantify CD8⁺/T_{reg} and CD4⁺/T_{reg} ratios in prostate specimens of treated patients.
- To quantify the extent of NK cell infiltration into the prostate from harvested prostate glands of treated patients.
- Enoblituzumab (MGA271) intraprostatic drug distribution in treated patients.
- To evaluate the proportion of pathological complete responses (pCR) in prostate tumor specimens of treated patients.
- To evaluate PSA response rates and the time-to-PSA-recurrence after radical prostatectomy in treated patients.
- To assess Gleason grade change post neoadjuvant Enoblituzumab treatment, comparing prostatectomy Gleason sum to pre-treatment biopsy Gleason sum

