4.2 Expected Enrollment

A total of 32 patients will be included in this study. The first patients are expected to be enrolled in February 2016, once the protocol has been approved by the IRB. With an estimated enrollment rate of 3 patients per month, accrual is expected to be completed in 5-6 months.

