10. STATISTICAL CONSIDERATIONS

10.1 Study Design and Sample Size

This is a single-center, single arm, open-label phase II study evaluating the safety, anti-tumor effect, and immunogenicity of neoadjuvant MGA271 given weekly for 6 doses beginning 50 days prior to radical prostatectomy in men with high-risk localized prostate cancer. Our primary objective is to characterize safety, tolerability, and feasibility of treatment of men with Enoblituzumab in the neoadjvuant setting. The trial will monitor toxicity and safety, as well as surgery related adverse events. (see Section 10.2.1). The secondary objective will be to evaluate immune response consistent with the agent's proposed mechanism of action (MOA), antibody-dependent cellular cytotoxicity (ADCC). Tumor cell death will be quantified by Caspase 3 staining, and post-treatment apoptotic index compared with that from the pre-treatment biopsy. The sample size is driven by detecting a pharmacodynamic effect of the agent based on the key secondary endpoint of tumor cell death. A biologically meaningful treatment effect will be deemed to be one where the tumor cell apoptosis is two-fold higher after MGA271 therapy. Previous study showed that baseline apoptosis, measured by Caspase staining, is 0.06 + - 0.08 (Mean + - SD) for Gleason 4 and 0.2 ± 0.2 for Gleason 3 (Kim et al. 2016). Based on this data, we assume that the coefficient of variation of tumor cell death measure is 1.2 and the correlations between the measures pre- and post-treatment is moderate at 0.4, 16 subjects will provide 88% power to detect a 2-fold increase in apoptotic tumor cells after the treatment compared to baseline, using a one-sided paired t-test with significance level 0.05.

In Amendment 1, the study was expended to enroll an additional 16 patients for a total of 32 patients to continue evaluating safety and better estimate the clinical benefit of Enoblituzumab in terms of undetectable PSA level (<0.1 ng/mL) at 12 months following radical prostatectomy.

Patients will be replaced if they are removed from the study after signing the informed consent but before undergoing radical prostatectomy. Patients receiving at least one dose of the study drug will be included in both safety and efficacy analyses.

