- **Regulatory T cell (T_{reg}) density**. The methods for analyzing T_{reg} infiltration will be similar to those described for CD8⁺ T cell infiltration. Descriptive statistics and graphical summaries will be provided. In addition, the CD8⁺/T_{reg} ratio and the CD4⁺/T_{reg} ratio will be computed, and reported using descriptive statistics.
- **CD4**⁺ **T cell density.** The methods for quantifying and analyzing CD4⁺ T cell infiltration will be similar to those described for CD8⁺ T cell infiltration. Descriptive statistics and graphical summaries will be provided.
- **Mean NK cell density**. The methods for quantifying and analyzing NK cell infiltration will be similar to those described for CD8+ T cell infiltration. Descriptive statistics and graphical summaries will be provided.
- **Tissue androgen concentrations**. Intraprostatic androgen concentrations (*i.e.* testosterone and dihydrotestosterone) will be summarized descriptively.
- **Enoblituzumab (MGA271) drug distribution**. Intraprostatic Enoblituzumab staining concentrations will be summarized descriptively.
- Androgen receptor (AR) quantification. Androgen receptor (AR) staining concentrations will be summarized descriptively.
- **Pathological complete responses (pCR)**. This will be defined as an absence of tumor identification on standard histological analysis of the resected prostate specimens.
- **PSA response rates**. This will be defined as an undetectable PSA (<0.1 ng/mL) at 3 months after prostatectomy. The proportion of patients achieving a PSA response will be reported. .
- **Time to PSA recurrence.** This will be defined as the interval from prostatectomy to the time when the serum PSA is ≥0.2 ng/mL. For subjects who have not yet demonstrated PSA recurrence at the time of censoring, patients will be censored at the date of the last

assessment that shows a lack of PSA recurrence. The median time to PSA recurrence after prostatectomy (*i.e.*, the median PSA-recurrence-free survival) will be estimated with 95% confidence intervals using Kaplan-Meier survival analysis.

• **Gleason grade change** post neoadjuvant Enoblituzumab treatment from pre-treatment biopsy. This will be calculated utilizing the highest Gleason grade from the pre-treatment biopsy and the post-treatment prostatectomy.

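### The Gleason endpoint is specified as an undirected proportion with any change, so read literally it cannot show whether grade moved down or up

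*Combined protocol and SAP*

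**What the plan says.** The secondary objective in section 1.2 is "To assess Gleason grade change post neoadjuvant Enoblituzumab treatment, comparing prostatectomy Gleason sum to pre-treatment biopsy Gleason sum". It names no direction.

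Section 8.3.19, headed as applying to the expansion cohort, describes the endpoint as "assessment of Gleason grade change (prostatectomy Gleason sum vs. core biopsy Gleason sum) post neoadjuvant Enoblituzumab treatment". Its text defines the comparison as the highest grade on the pre-treatment biopsy against the highest grade at prostatectomy, and gives the summary measure: "This endpoint will be expressed as the proportion of men achieving a Gleason score change".

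Section 10.2.2 adds only the inputs: "This will be calculated utilizing the highest Gleason grade from the pre-treatment biopsy and the post-treatment prostatectomy". It names no direction, size of change, interval, shift table or test. The synopsis entries for this endpoint repeat the objective and add nothing on direction. The synopsis statistical methods also say that endpoints other than those driving the sample size are exploratory and will be described only.

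**The concern.** Each man contributes a pair of ordinal readings, so his change has a sign and a size. The stated summary keeps neither. Taken at its word, a man going from 9 to 7 and a man going from 7 to 9 are both counted. Entry requires "Gleason sum 7-10", so movement in both directions is possible for most men.

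The study looks for anti-tumour effects, and a reader will want to know whether grade fell or rose after treatment. An undirected proportion takes the same value for a cohort that was mostly downgraded, one that was mostly upgraded, and one in which cores and gland simply disagreed at random. If the text is left as it is, the direction or cut-off could be chosen after the results are known, in an open-label single-arm trial.

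**Working it through.** The plan states no rate, threshold, power or sample size for this endpoint, so there is no figure to reproduce. The check has two parts.

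**1. Search for a direction.** The synopsis (objectives and criteria for evaluation), section 1.2, section 8.3.19 and section 10.2.2 all mention the endpoint. None defines change as downgrading, separates it from upgrading, sets a minimum change, or plans a paired ordinal summary. The text also moves between Gleason sum, grade and score, but direction is missing under each of these readings.

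**2. What the stated summary can show.**

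Inputs:
- N = 32 from section 4.2: "A total of 32 patients will be included in this study". N = 16 is shown as well, because the heading of 8.3.19 refers to the expansion cohort and the expansion adds 16 men.
- The number of men changed is **assumed**, since the documents give no discordance rates: 12 of 32, or 6 of 16 (the same 37.5%).

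Formulas, with D men down and U men up:
- Endpoint as written = (D + U)/N.
- By direction: D/N and U/N; net = (D − U)/N.
- Exact (Clopper-Pearson) 95% limits for x of N: lower = Beta quantile 0.025 with parameters (x, N − x + 1); upper = Beta quantile 0.975 with parameters (x + 1, N − x). For x = 0 the lower limit is 0 and the upper is 1 − 0.025^(1/N), which is 10.9% at N = 32 and 20.6% at N = 16.

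| N | Down / up | Endpoint as written (95% CI) | Downgraded (95% CI) | Upgraded (95% CI) | Net down |
|---|---|---|---|---|---|
| 32 | 12 / 0 | 37.5% (21.1–56.3) | 37.5% (21.1–56.3) | 0% (0–10.9) | +37.5 points |
| 32 | 6 / 6 | 37.5% (21.1–56.3) | 18.8% (7.2–36.4) | 18.8% (7.2–36.4) | 0 |
| 32 | 0 / 12 | 37.5% (21.1–56.3) | 0% (0–10.9) | 37.5% (21.1–56.3) | −37.5 points |
| 16 | 6 / 0 | 37.5% (15.2–64.6) | 37.5% (15.2–64.6) | 0% (0–20.6) | +37.5 points |
| 16 | 3 / 3 | 37.5% (15.2–64.6) | 18.8% (4.0–45.6) | 18.8% (4.0–45.6) | 0 |
| 16 | 0 / 6 | 37.5% (15.2–64.6) | 0% (0–20.6) | 37.5% (15.2–64.6) | −37.5 points |

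The fourth column is constant within each N, while the net shift runs across the full range that the number of changed men allows. The assumed counts set the level of the figure. The loss of direction does not depend on them.

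**The case against.** **The wording may intend improvement.** Sections 8.3.16 and 8.3.17 use the same sentence pattern, with the verb for achieving attached to a favourable event (a pathological complete response, a PSA response). A Gleason change that is achieved may therefore mean a downgrade. Section 10.2.2 does not repeat the proportion, and a change calculated from two grades would normally carry a sign. This stands in part: it is not certain that upgrades were meant to count. But the neighbouring sections name and define their event, and 8.3.19 names only a change. If downgrading was meant, the text has to say so, and downgrades reported alone would still leave out the upgrades.

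**Direction can be recovered.** Both readings are kept for every man. This is true, and it is why the repair costs so little. It does not replace stating the summary in advance.

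**The endpoint is descriptive.** This is also true. It drives no sample size, stopping rule or primary conclusion, which limits the importance of the point.

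**A stronger reading: lost power.** A reader might infer that the trial gives up power and should run a sign or Wilcoxon signed-rank test of down against up. The documents do not support this. They plan no test, null rate or significance level for Gleason change, so there is no power to lose, and any power figure would rest on invented discordance rates and an invented test. The proposed test also has a null of its own to defend: that without the drug, movement up and down is equal. Section 10.1 states "This is a single-center, single arm, open-label phase II study". Men enter on a biopsy Gleason sum of at least 7, and needle cores are compared with a whole gland, so untreated discordance need not be symmetric. To show what this can do, suppose the no-drug pattern were 30% down and 10% up (assumed). A one-sided 5% sign test would then reject about 47% of the time at N = 32, and about 19% at N = 16, with no drug effect at all.

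**Conclusion.** The point holds as a gap in the specified summary. Sections 8.3.19 and 10.2.2 leave the direction and size of Gleason change undefined, and the literal reading gives one figure for cohorts that moved in opposite directions. In the illustration that figure is 37.5% while the net shift ranges from +37.5 to −37.5 points. The 12 of 32 is an assumption used for arithmetic. Whether the denominator is 32 or 16 is not settled by the text, and the conclusion is the same for both.

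Two further inferences should not be drawn. The documents do not show that upgrades were deliberately meant to count as successes; they leave the matter open. Nor would a directional report establish a drug effect: with no control arm, a shift between cores and gland cannot by itself be attributed to treatment. The consequence is confined to one secondary descriptive endpoint, and the change is a cheap improvement.

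**What to change.** In 8.3.19 and 10.2.2, replace the undirected proportion with wording such as: *The number and proportion of men downgraded, unchanged and upgraded from biopsy to prostatectomy will be reported, each with an exact 95% confidence interval, together with a shift table of biopsy by prostatectomy Gleason. Men with no gradable tumour at prostatectomy (pCR) will be shown as a separate category. The analysis is descriptive.*

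State the denominator (all 32 men or the 16 added), and use one Gleason measure throughout. Add no sign or signed-rank test.

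The cost is protocol wording only. The same two pathology readings are used, with no new data, patients or procedures. The downside is that three proportions and a small table are reported in place of one figure.

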9. REGULATORY AND REPORTING REQUIREMENTS

Contact details for personnel connected with this study are provided on the title page at the front of this protocol. Patient registration procedures are described in Section 4.

9.1 Regulatory Responsibilities

9.1.1 Protocol chair

The protocol chair (=PI) is responsible for the following tasks:

- Coordinating, developing, writing, submitting, and obtaining IRB-approval for the protocol as well as its subsequent amendments.
- Assuring that all study personnel are using the correct version of the protocol.
- Taking responsibility for the overall conduct of the study and for monitoring the progress of the study.
- Reviewing and ensuring reporting of serious adverse events (SAEs).
- Reviewing data from all patients.

9.1.2 Study Coordinator

The study coordinator is responsible for the following tasks:

- Ensuring that IRB approval has been obtained prior to patient registration, and maintaining copies of IRB approvals (including approval of amendments).
- Managing patient registration.
- Collecting and compiling data from each patient.

Protocol Version 2.0 (Amendment 2) / Version Date: 04/17/2019

- Establishing procedures for documentation, reporting, and submission of AEs/ SAEs to the protocol chair (Name) and other applicable parties.
- Facilitating audits by securing selected source documents and research records from participating patients for audit.

9.1.3 Study personnel

Study personnel (co-investigators, research nurses) are responsible for these tasks:

- Following the protocol as written, and Good Clinical Practice (GCP) guidelines.
- Submitting data to the project manager.
- Registering all patients by submitting the patient registration form and signed informed consent form promptly.
- Providing sufficient experienced clinical and administrative staff and adequate facilities and equipment to conduct the trial according to the protocol.
- Maintaining regulatory binders and providing copies of all required documents to the project manager.
- Collecting/submitting data according to the schedule specified by the protocol.

9.2 Data Management

Data collected during this study will be entered into a secure database. The study coordinator will be responsible for the initial study configuration and setup of the database and for any future changes.

9.2.1 Case report forms

Case report forms (CRFs) will be generated by the study coordinator for the collection of all study-related data. Investigators and study personnel will be responsible for ensuring that the CRFs are kept up-to-date.

